## VI. Statistical Analysis

- a) *Statistical Plan:* The Mann-Whitney U test will be used to analyze differences in changes of QEEG between responders and non-responders to CBT. We will use logistic regression with the outcome being response/no response on the HAMD-17 and the predictors being other EEG measures. We will test the predictors in a stepwise manner given the limited power with a small N. A power calculation based on a previous QEEG study conducted in our clinic reveals that, to achieve power = 0.80, we would need 34 subjects per group. With N = 30 per group (60 subjects total), our power is 0.76. Power for the current study, with N = 15 per group, is 0.47. While this study is underpowered due to the small N, the goal of this study is to act as a pilot study which can help measure effect sizes, providing a foundation for future, larger projects.

For secondary aims, we will use Pearson r's for pairs of continuous measures, or point-biserial r for pairs of dichotomous and continuous measures.

Data from the Signal Detection Fact Task will be analyzed by [name] at Harvard University. Response bias will be the main variable of interest, whereas reaction time, hit rates, and discriminability values will provide control variables. Analyses of variance (ANOVAs) will be used to investigate variables across the three blocks. Discriminability and response biases will be computed using standard formulae (e.g. McCarthy and Davidson 1981).

- b) *Study Endpoints:* Endpoints will be defined as the final study visit at the end of the 12 weeks, or the termination/final visit for patients who choose to (or have to) end participation in the study prematurely.

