#### **IV. Subject Enrollment**

*A. Methods of enrollment/registration/randomization:*

Patients are usually screened by telephone to determine tentative eligibility for studies. The subjects then are invited to come to MGH for a full psychiatric diagnostic interview. Patients accepted into the study will be registered through the Depression Clinical and Research Program. Randomization numbers will be provided by the study Biostatistician and will be maintained by the research pharmacists at MGH Research Pharmacy, who will administer the open label escitalopram, 10-20 mg/day, to those subjects who have been randomized to receive medication. The randomization will be 1:1, i.e. half of the patients will be randomized to receive escitalopram (10-20 mg/day, flexible dose) and half will be randomized to receive twelve weekly 50-minute

Cognitive Behavioral Therapy sessions. Both treatment interventions have been strongly validated by the literature, and are considered standard of care for this population.

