## V. Study Procedures

### a) *Study visits and parameters to be measured:*

The study involves the enrollment of 30 outpatients with major depressive disorder.

Patients screened for the study and found to be eligible will return for their baseline visit after one week, at which eligible patients (n = 30) will be randomized to either CBT or to standard pharmacotherapy with an SSRI (escitalopram 10-20mg) for 12 weeks.

The CBT group will receive twelve weekly 50-minute individual sessions over the course of 12 weeks conducted by experienced therapists who are trained in manual based CBT. The medication group will receive open label treatment of escitalopram, 10-20 mg/day, flexible dose, for 12 weeks, and will be seen every two weeks by a study physician. In both arms, study assessors, who are blind to treatment condition, will assess patients monthly (week 0, 4, 8, and 12), and are responsible for the primary outcome measure (HAMD-17).

The QEEG will be administered 5 times during the study (week 0, 1, 2, 8 and endpoint) allowing us to assess whether there are any correlations between QEEG patterns and changes in clinical functioning. We will record EEG from a fronto-parieto-temporal derivation using a 4-channel EEG Monitor (Aspect Medical Systems) connected to the subject via disposable EEG electrodes. The adhesive material of the electrodes is similar to that found in ECG electrodes. All recordings will be analyzed off-line to generate QEEG metrics. Once such QEEG metric, the ATR, is a complex index derived from left-right asymmetry of combined theta+alpha (4-12Hz) power, relative theta power, and percent change from baseline in relative theta power, and ranges from 0 (low probability of response) to 100 (high probability of response). De-identified data will be shared with Aspect Medical Systems for offline calculation of EEG-based metrics.

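### Unpenalised logistic regression in a CBT arm of about 15 patients would overstate real odds ratios on average and occasionally have no finite estimate, which undermines the pilot's effect-size goal

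*Protocol*

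**What the plan says.** Protocol section VI, a) Statistical Plan, starts with a Mann-Whitney comparison of QEEG change between responders and non-responders to CBT. It then states: "We will use logistic regression with the outcome being response/no response on the HAMD-17 and the predictors being other EEG measures". The sentence after that has the predictors tested stepwise because the sample is small. No estimator, penalised or exact method, number of predictors or rule for separation is given, and the logistic sentence names no arm.

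On size, section V says "The study involves the enrollment of 30 outpatients with major depressive disorder" and section IV says "The randomization will be 1:1, i.e. half of the patients will be randomized to receive escitalopram", so each arm has about 15 patients before dropout. Section II names at least three metrics: ATR, bispectrum and cordance.

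Section VI concedes low power ("Power for the current study, with N = 15 per group, is 0.47") and justifies the study because "the goal of this study is to act as a pilot study which can help measure effect sizes". It does not mention biased or non-finite estimates.

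The SAP contains no logistic model. It describes t tests of QEEG change by response status, in completers.

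**The concern.** Logistic regression with no qualifier ordinarily means maximum likelihood. In small samples the ML log odds ratio for a real effect is biased away from zero. If some combination of predictors places all responders on one side and all non-responders on the other (separation), the likelihood has no maximum at finite coefficients. Both problems exist with a fixed predictor list, and even with a single predictor.

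The plan defends its small sample as a way to gauge effect sizes, so bias in the estimate matters here as well as low power. If an inflated odds ratio were carried forward, the larger study would be planned too small. A non-finite estimate could be reported as perfect prediction, or dropped without comment.

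**Working it through.** **1. An effect size consistent with the plan.** The documents give no effect size, alpha or sidedness. They give three linked figures: "to achieve power = 0.80, we would need 34 subjects per group"; "With N = 30 per group (60 subjects total), our power is 0.76"; and 0.47 at 15 per group. I assume two-sided alpha 0.05 and a normal-approximation comparison of two means, with power = Φ(d√(n/2) − 1.96). Taking d = 0.688:

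- n = 15: 0.688 × √7.5 = 1.884; Φ(−0.076) = 0.47.
- n = 30: 0.688 × √15 = 2.665; Φ(0.705) = 0.76.
- 80% power: n = 2(1.960 + 0.842)²/d² = 15.70/0.473 = 33.2, rounded up to 34.

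All three stated figures are reproduced. For equal-variance normal predictors the logistic coefficient per SD equals d, so the assumed true log odds ratio is 0.69 (odds ratio 2.0). The plan does not say which two groups its power refers to, so 0.69 is only a plausible value.

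**2. Simulation.** There were 1,200 to 20,000 data sets per setting. One predictor had true log odds ratio 0.69, and any others were null and independent. Response was assumed to be 33–50% (about 5 to 8 of 15), because the documents give no rate. Separation was detected by linear programming. ML means and medians are over finite fits; ranges span runs and response splits.

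| Setting | ML mean | ML median | Separation |
|---|---|---|---|
| 15 patients, 1 predictor | 0.97–1.03 | 0.80–0.82 | 0.3–1.4% |
| 15 patients, 3 predictors | 1.22–1.33 | 0.90–0.94 | 5–12% |
| 15 patients, 5 predictors | 1.51 | not tabulated | 31–41% |
| 12 completers, 1 predictor | 1.16 | 0.80 | 3% |
| 12 completers, 3 predictors | 1.24 | 0.89 | 15–22% |
| 30 pooled, 1 to 3 predictors | 0.80–0.91 | about 0.74 (1 predictor) | essentially nil |

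With one predictor, a mean of 1.02 is 1.02/0.69 = 1.48 times the truth. The median of 0.80 corresponds to an odds ratio of e^0.80 = 2.2 against 2.0. When the true odds ratio is 1 there is no systematic direction of bias, only scatter (SD 0.93 with one predictor).

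**3. Firth's method.** This maximises ℓ(β) + ½ log|I(β)|, where I is the Fisher information, and always gives a finite estimate. Its mean was 0.66–0.78 across the 15-patient settings and 0.69–0.72 at 30.

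- Root mean squared error, 7/8 split: 0.63–0.66 against 0.98–1.04 for ML with one predictor; 0.78–0.89 against 1.63 with three.
- Estimates more than double the truth, or infinite: ML 26% with one predictor and 35% with three; Firth 13% and 16%.

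**4. Stepwise selection.** I simulated a first forward step (15 patients, 40% response, likelihood-ratio p < 0.05; 1, 3 or 6 candidates). The selected ML coefficient had median |log odds ratio| 1.8–2.0 when the informative predictor's true value was 0.69. Using Firth with a Wald p < 0.05, only about 2% of runs selected anything, and those coefficients had median 1.9–2.1. The two entry tests differ, so the selection rates are not comparable. What the runs show is that penalisation alone does not remove selection inflation.

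**5. Consequence if the coefficient is carried forward.** Using the formula in step 1, planning on 0.80 gives 15.70/0.64 = 24.5, so 25 per group, with power at the true 0.688 of Φ(0.688 × √12.5 − 1.96) = 0.68. Planning on 1.03 gives 15.70/1.061 = 14.8, so 15 per group, with power 0.47.

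**The case against.** A reader might infer that the model defeats the pilot's purpose, or that ML overstates every non-zero coefficient. Neither is supported.

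- **Other effect sizes exist.** The protocol never says odds ratios are the effect sizes it means. The Mann-Whitney contrast, and the SAP's t tests on the same kind of contrast, allow a standardised difference that does not depend on the logistic model. This stands.
- **The bias is an average.** With one predictor and a 7/8 split, 43% of finite ML estimates fell below the truth. A skewed tail pulls up the mean. The median shift is 0.80 − 0.69 = 0.11, against a median standard error of 0.66, and nominal 95% Wald intervals covered the truth in about 98% of finite fits. This stands for one moderate predictor.
- **Separation is rare with one metric per model.** This is true at 15 patients and a moderate effect. It rises to 7–10% if the true log odds ratio is 1.5, and to 6% with 10 completers.
- **Estimator and arm are inferred.** This is correct. Primary Aim 1 and the preceding Mann-Whitney sentence concern CBT, so that arm is the natural reading. A pooled model would have much less of the problem.
- **Stepwise testing inflates more.** This is also correct, so a change of estimator alone is not enough.
- **Firth does not make 15 patients informative.** Its median is 0.62–0.65, slightly below the truth, and its SD with one predictor is still about 0.67–0.75. Even so, total error is lower than with ML in the settings compared.

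**Conclusion.** The concern holds in a limited form. If the logistic model is fitted by ordinary ML in about 15 CBT patients, real effects are overstated on average. The excess is modest at the median with one predictor and larger with three or more, where separation also becomes a practical problem. The plan has no safeguard against either. This undermines, but does not defeat, the aim of helping to measure effect sizes.

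The conclusion rests on reading the estimator as ML and the arm as CBT, and on assumed values for the true effect, response rate and number of predictors, none of which the documents give. It concerns the protocol's plan. The documents do not support a claim that the SAP's t-test results are affected. The change is worth making because it is cheap and reduces both mean bias and total error.

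**What to change.** In protocol section VI, a) Statistical Plan:

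- Name the arm in the logistic sentence.
- Replace logistic regression by Firth penalised-likelihood logistic regression, with profile penalised-likelihood confidence intervals.
- In the 15-patient arm, fit one pre-specified EEG metric per model.
- Delete the sentence on stepwise testing.

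Possible wording: *Within the CBT arm, response on the HAMD-17 will be related to each pre-specified EEG metric in a separate Firth penalised-likelihood logistic regression, reported as an odds ratio per SD with a profile penalised-likelihood 95% confidence interval. No data-driven selection of predictors will be used.*

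The SAP needs matching text only if odds ratios are added or reported.

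The cost is a few sentences, a pre-specified list of metrics and a standard software option. The odds ratios will be less extreme, the median estimate will fall slightly below the truth, and the intervals will remain wide.

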Quantitative Electroencephalogram (QEEG) Predictors of Response to Psychotherapy
Versus Antidepressant Treatment in Depression

Identifiers: NCT00824044

Unique Protocol ID: 2008-P-000838

Date prepared: 12/7/2017

Summary:

A-priori expectation from prior **medication** work is a decrease in theta activity from baseline at week 1 in responders, and an increase in non-responders. Prior work showed an increase in theta activity in **placebo** responders (and little change in non-responders). (See attached manuscript that describes changes in theta Cordance over time in both placebo and medication groups. See Fig 4 on page 128.) Also, ATR is expected to be higher in medication responders than non-responders after 1 week on antidepressant.

Methods:

ATR and Power metrics were calculated from available EEGs at baseline and subsequent visits. Change in Power between baseline and subsequent visits were derived. The data were analyzed for 3 groups: Pooled, Drug-only, Drug+CBT.

In a completer analysis (not an intent to treat), independent sample t tests were used to assess the relationship between responders (greater than or equal to 50 % reduction in the primary outcome (HAMD-17 score)) and change in QEEG metrics across time.

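### The protocol justifies stepwise selection on unlisted EEG measures by small N, which would bias the effect sizes the pilot is meant to supply; the SAP replaces the protocol's methods without a reason and names no CBT-only comparison

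*Protocol*

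**What the plan says.** Protocol section VI gives two analyses of QEEG against response. The first is a rank test: "The Mann-Whitney U test will be used to analyze differences in changes of QEEG between responders and non-responders to CBT". The second is a logistic regression of HAMD-17 response, with "the predictors being other EEG measures", and the instruction "We will test the predictors in a stepwise manner given the limited power with a small N". No list of those measures, entry or removal rule, or analysis population (CBT patients or all patients) is given. The same paragraph admits low power and says the study is to "act as a pilot study which can help measure effect sizes, providing a foundation for future, larger projects".

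Hypothesis 1 (protocol section II) names three metrics, ATR, EEG Bispectrum and cordance, and one window, baseline to week 2. Primary Aim 1 concerns response to CBT.

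The SAP's Methods paragraph reads differently. On metrics: "ATR and Power metrics were calculated from available EEGs at baseline and subsequent visits". On groups: "The data were analyzed for 3 groups: Pooled, Drug-only, Drug+CBT". On the test: "In a completer analysis (not an intent to treat), independent sample t tests were used". Its Summary sets out expectations for medication and placebo. For ATR it says "ATR is expected to be higher in medication responders than non-responders after 1 week on antidepressant".

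**The concern.** Small N is offered as the reason for stepwise testing. It is a reason to limit the number of predictors, but not to let the data choose them. With few patients, a measure enters only if its observed effect is large, so the effect read from the final model is too big on average, and the measure chosen may be the wrong one. That matters here because the pilot's stated product is effect sizes. A follow-up study planned on a selected estimate would be too small.

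The second difficulty is that the two documents do not describe the same analysis. A reader who wants the planned test of CBT response finds a Mann-Whitney test and a stepwise model in the protocol. The SAP has t tests in three groups, none labelled CBT alone, with no explanation of the change.

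**Working it through.** **Inputs.** From protocol section VI: 34 per group for power 0.80, power 0.76 at 30 per group, and 0.47 at 15 per group. From sections IV and V: 30 patients randomized 1:1, so 15 per arm. From Hypothesis 1: three metrics. Not given, and therefore assumed: two-sided alpha 0.05, effect size, responder split, entry rule, candidate set, and correlation between metrics.

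**1. Reproduce the plan's power figures.** Normal approximation: d = (1.960 + 0.842) × √(2/34) = 0.68. Power at n per group is Φ(d√(n/2) − 1.96), which gives 0.80, 0.749 and 0.461 at n = 34, 30 and 15. The noncentral t with d = 0.69 gives 0.80, 0.747 and 0.446. A common d of 0.694 to 0.707 under the t test brings all three within two points of the stated values. The figures are therefore consistent with a standardized effect near 0.69, which is used below as the true responder contrast.

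**2. The entry bar.** For a score test at p<0.05, a first predictor enters only if N·r² > 3.841. At 7 v 8, r² > 3.841/15 = 0.256, so t > √(0.256 × 13/0.744) = 2.12 and |d| > 2.12 × √(1/7 + 1/8) = 1.09. At 15 v 15 the same steps give |d| > 0.74. Both bars lie above the assumed true effect of 0.69.

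**3. Size of the bias.** Simulation, 40,000 runs per setting: three candidates, one with d = 0.69 and two null, inter-metric correlation 0 to 0.8, score-test entry. The entries are the mean absolute d of the first metric to enter. Ratios are to the unselected mean absolute d of the predictive metric.

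| Entry rule | 7 v 8 (unselected 0.78) | Ratio | 15 v 15 (unselected 0.72) | Ratio |
|---|---|---|---|---|
| p<0.05 | 1.47–1.48 | 1.9 | 1.04 | 1.4 |
| p<0.10 | 1.29 | 1.7 | 0.94–0.95 | 1.3 |
| p<0.25 | 1.07–1.10 | 1.4 | 0.83–0.85 | 1.2 |

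At p<0.05 a metric enters in only about 29–33% of runs (7 v 8) or 49–51% (15 v 15). When all three candidates are noise, at least one enters in about 11–16% of runs (7 v 8) or 10–15% (15 v 15) at p<0.05. At p<0.10 the figure is about 20–31% across both sizes.

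**4. Where the bias comes from.** At 7 v 8, one prespecified metric kept only if p<0.05 averages about 1.49. Taking the best of three with no threshold averages 0.92–0.96. Both exceed 0.78, so the threshold and the search each contribute.

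**5. Consequence for a follow-up.** Required n scales roughly as 34 × (0.69/d)². At d = 0.83 this is 34 × 0.691 = 23.5, so 24 per group. At d = 1.48 it is 34 × 0.217 = 7.4, so 8 per group.

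**6. The two documents side by side.**

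| | Protocol | SAP |
|---|---|---|
| Test | Mann-Whitney; stepwise logistic | Independent-sample t tests |
| Group for Aim 1 | CBT patients (Mann-Whitney); unstated (logistic) | Pooled, Drug-only, Drug+CBT; none labelled CBT alone |
| Metrics | ATR, Bispectrum, cordance (Hypothesis 1); unlisted others (logistic) | ATR and Power metrics |
| Time | Change to week 2 (Hypothesis 1) | Across time; week 1 the only time named |
| Primary metric and time | Not designated | Not designated |

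**The case against.** The protocol calls the study underpowered and a pilot. It gives no entry rule, so a stepwise manner could mean testing predictors one at a time in a fixed order, and limiting predictors per model is a sensible response to small N. The later SAP, written in the past tense, contains no stepwise model, so the bias may never have arisen. The Mann-Whitney comparison is unaffected if it is reported for every metric. In the scenario above, at p<0.05, nothing enters in about half to two thirds or more of runs, and then there is no inflated estimate to carry forward. The power statement can be read as comparing treatment arms, so d = 0.69 may not describe a responder contrast.

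Much of this stands and limits the claim. It does not remove it. A fixed order would need to be stated, and none is. The pilot label answers a complaint about false positives but not one about biased effect sizes, since effect sizes are the stated goal. If the model was abandoned, the SAP should say so.

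A reader might infer several stronger things that the documents do not support:
- That the SAP names no test. It names t tests; what is missing is a primary metric and time point.
- That entry is at p<0.05. No rule is given, and the bias shrinks as the rule loosens.
- That the threshold alone causes the inflation. Step 4 shows that the search adds to it.
- That cordance was dropped. It appears only in the SAP's account of prior work, but the protocol's Background section describes it as built from signal power, so Power metrics may include it. Bispectrum is not named at all.
- That stepwise results were produced or selectively reported. Nothing shows this.

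**Conclusion.** The point holds in conditional form. If stepwise means data-driven selection, the protocol's reason for it runs the wrong way, and estimates read from the selected model would be inflated about 1.2 to 1.9 times over the settings examined. That conflicts with the study's stated purpose. The multiple rests on a back-solved d of 0.69 applied to a responder contrast, three candidates with one predictive, near-even responder splits, no dropout and score-test entry. The direction of the bias persists at every entry rule tried.

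The discrepancy between the documents needs none of those assumptions. The SAP replaces both protocol methods without a reason, designates no primary metric or time point, and labels no CBT-only group for a primary aim about CBT. Its stated expectations are for medication and placebo. This should be corrected, but it does not invalidate a declared pilot.

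**What to change.** 1. Protocol section VI: delete the stepwise sentence. If logistic models are kept, fit one prespecified predictor at a time.
2. SAP: state which test governs Aim 1 and why it differs from the protocol, and add a CBT-only comparison of responders with non-responders.
3. Report that comparison for change to week 2 for ATR, EEG Bispectrum and cordance, each with an effect size and confidence interval whatever its p-value. If a metric was not calculated, say so.
4. Label all other metrics, visits and groups exploratory and report them in full.

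The cost is one deleted sentence, a few lines in the SAP, and possibly some offline calculation from stored recordings. The drawback is that no best-predictor model results and the intervals are wide. At d = 0.69 and 7 v 8, the standard error is √(15/56 + 0.69²/26) = 0.535, so the 95% interval is about −0.36 to 1.74.

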## **II. Specific Aims:**

Primary Aim 1: To determine whether QEEG technology can predict whether a patient with MDD will respond to CBT.

Hypothesis 1: Clinical response (defined as >50% change in HAMD-17 from beginning to endpoint) will correlate with changes in QEEG metrics (ATR, EEG Bispectrum, cordance estimates) from beginning to two weeks after starting treatment.

Primary Aim 2: To determine whether there are unique biological changes in patients undergoing CBT, as measured by the QEEG, that are different than those associated with antidepressants (SSRIs).

Hypothesis 2: QEEG parameters, different from those that predict response to pharmacotherapy, will be associated with response to CBT.

Secondary Aim 1: To determine whether there are correlations between QEEG patterns and changes in clinical functioning, assessed by clinical and self-rated instruments (SF-36, Symptom Questionnaire, Beck Depression Inventory), in both arms (CBT vs. escitalopram).

Secondary Aim 2: To determine whether there are any correlations between QEEG metrics and clinical variables (gender, age, comorbid anxiety, chronicity of depression).

Secondary Aim 3: To determine whether the behavioral processes associated with reward responsiveness in a depressed population change as a function of treatment.

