The Signal Detection Task will be administered at baseline and at endpoint. In the specific Signal Detection Task we will use, called the Face Game (assessing reward sensitivity), we will present simple cartoon faces (diameter: 25 mm; eyes: 7 mm) in the center of the monitor and at the beginning of the trial. The face has no mouth. After a given delay, either a straight mouth of 11.5 mm (“short mouth”) or 13 mm (“long mouth”) will be presented for 100 ms. Subjects will be instructed to press an appropriate button to decide whether a long or short mouth had been presented. For the present study, the experiment will consist of 300 trials, divided into 3 blocks of 100. Long and short mouths will be presented equally often. A trial will begin with the presentation of an asterisk for 500 ms that will serve as fixation point and warning stimulus that a trial will start. After 500 ms, a mouth-less face will be presented and will stay on the screen until a response is made; after an inter-stimulus interval of 500 ms, one of the two mouths will be presented for 100 ms. Critically, not all correct responses will receive feedback (only positive feedback will be provided). For each block, 40 correct trials will be followed by a reward feedback (“Correct!! You won 5 cents”), presented for 1750 ms immediately after the correct response. For half of the subjects, correct identification of the little mouth will be associated with three times more positive feedback (30/40) than correct identification of the big mouth (10/40). For the other half of the subjects, the contingencies will be reversed. After feedback, an inter-trial interval (ITI) of 250 ms will follow. Subjects will be instructed that the aim of the study is to win as much money as possible, and that they will receive the amount of money won at the end of

experiment (actual money will be shown to the subjects for increasing the credibility of the experiment).

Scales:

Once the patient has agreed to participate in the study by signing the informed consent, the following instruments will be administered by a study assessor who is blind to treatment condition at screen, baseline, and visits 4, 8 and 12:

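### Secondary Aim 1 plans only a simple correlation of QEEG with change in BDI, SQ and SF-36; a baseline-adjusted estimate should stand beside it

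*Protocol*

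**What the plan says.** Secondary Aim 1 (Protocol, II. Specific Aims) looks, in both arms, for "correlations between QEEG patterns and changes in clinical functioning, assessed by clinical and self-rated instruments (SF-36, Symptom Questionnaire, Beck Depression Inventory"). The method is in Protocol VI, Statistical Plan: "For secondary aims, we will use Pearson r's for pairs of continuous measures", with a point-biserial r where one of the two measures is dichotomous. No covariate, partial correlation or regression is named for the secondary aims. The SAP describes only t tests of QEEG change between HAMD-17 responders and non-responders, so it adds nothing for this aim.

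The baseline scores exist. Protocol V has the scales "administered by a study assessor who is blind to treatment condition at screen, baseline, and visits 4, 8 and 12".

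Two definitions are missing. The protocol does not say whether change on these scales is a difference or a percentage; the only change it defines is the proportional HAMD-17 response. It also does not say which QEEG value enters the correlation, although "The QEEG will be administered 5 times during the study (week 0, 1, 2, 8 and endpoint").

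On size: "The study involves the enrollment of 30 outpatients with major depressive disorder", randomised 1:1, so about 15 per arm.

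**The concern.** A difference score contains the baseline score with a negative sign, so patients who start worse tend to show larger falls through regression to the mean alone. If a QEEG metric tracks severity at entry, it can correlate with the fall even though it says nothing about the endpoint beyond what the baseline score already says. A severity marker could then be read as a marker of improvement.

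The protocol makes a QEEG-severity link plausible without giving its size. Its background section reports lower cordance in MDD than in normal subjects, and Secondary Aim 2 itself looks for QEEG links with comorbid anxiety and chronicity. The study is a pilot meant to supply effect sizes for larger work. A correlation that mixes entry severity with improvement is a poor input for that, and in arms of 15 any avoidable loss of precision matters.

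**Working it through.** **The plan's own figure.** No power is stated for Secondary Aim 1. The stated power (0.80 at 34 per group, 0.76 at 30, 0.47 at 15) belongs to the group comparison. Assuming two-sided alpha 0.05, 34 per group at 0.80 implies d = (1.960 + 0.842)/√(34/2) = 0.68. Power at 15 is then Φ(0.68 × √7.5 − 1.96) = 0.46, and at 30 it is 0.75. The figures are internally consistent to about one point, but they do not bear on this aim.

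**Assumptions, none of them in the documents.** ρ is the baseline-endpoint correlation, c the QEEG-baseline correlation, k the ratio of endpoint SD to baseline SD. Change is endpoint minus baseline. Tests are two-sided at 0.05.

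**1. Carry-over when QEEG is linked to baseline only.** With the baseline SD set to 1, cov(QEEG, change) = c(ρk − 1) and var(change) = 1 + k² − 2ρk, so

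r(QEEG, change) = c(ρk − 1)/√(1 + k² − 2ρk).

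For k = 1 this reduces to −c√((1 − ρ)/2). With c = 0.4:
- ρ = 0.3: −0.4 × √0.35 = −0.24
- ρ = 0.5: −0.4 × √0.25 = −0.20

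Simulated rejection rates at k = 1, c = 0.4:

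| n | ρ | simple r with change | baseline-adjusted |
|---|---|---|---|
| 15 | 0.3 | 14% | 5% |
| 15 | 0.5 | 11% | 5% |
| 30 | 0.3 | about 25% | 5% |
| 30 | 0.5 | 19% | 5% |

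**2. Where the carry-over shrinks.**
- Weak link: at c = 0.2, n = 15, rejection is about 6% to 7%. At c = 0.1 the induced r is at most 0.06 in size and rejection is 5% to 6%.
- High ρ: at c = 0.3, k = 1, n = 15, rejection falls from 10% (ρ = 0.3) to 8% (0.5) and 7% (0.7).
- Larger endpoint SD: at k = 1.5, ρ = 0.5, c = 0.4, r = 0.4 × (0.75 − 1)/√1.75 = −0.08 and rejection at n = 15 is 6%. At k = 1.5, ρ = 0.3 it is 8%.
- The induced r is exactly zero when ρk = 1, for example k = 2, ρ = 0.5. Beyond that point it changes sign: k = 2, ρ = 0.7, c = 0.3 gives +0.08.

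**3. Precision when QEEG is unrelated to baseline.** At k = 1, residual variance over change variance is (1 − ρ²)/(2(1 − ρ)) = (1 + ρ)/2, which is 0.65 at ρ = 0.3 and 0.75 at ρ = 0.5. For a true partial r of 0.5, the correlation with change is 0.5 × √0.65 = 0.40 or 0.5 × √0.75 = 0.43. Fisher z power at n = 15 is 0.45 adjusted, against these values for the simple r:

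| ρ | 0.3 | 0.5 | 0.7 | 0.9 |
|---|---|---|---|---|
| power, simple r | 0.32 | 0.36 | 0.41 | 0.45 |

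The gain from adjustment is 13, 8 and 4 points, then nothing. With the effect set instead at 0.5 endpoint SD per SD of QEEG, n = 15 power is 0.36 simple against 0.52 adjusted (ρ = 0.3), and 0.50 against 0.62 (ρ = 0.5). At k = 1.5 and ρ = 0.5 the advantage is gone (0.64 simple, 0.62 adjusted).

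**4. The adjusted estimate can also mislead.** Suppose true severity does not change, baseline and endpoint scores differ only by measurement noise, and QEEG correlates 0.3 to 0.5 with true severity. The simple r with change holds 5%. With score reliability of 0.5 to 0.7, the adjusted test rejects about 7% to 12% at n = 15 and 9% to 21% at n = 30, because a noisy baseline score removes only part of the severity link.

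**The case against.** The strongest case against has four parts.

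- **The aim asks about change, and a correlation with change answers it.** The endpoint given baseline is a different quantity, and because QEEG is not randomised neither analysis is free of bias in general. This stands. It is why the adjusted estimate should be added and should not replace the simple r.
- **The plan does not say raw change.** A reader might infer that it does, but the documents leave change undefined. The argument holds only if change is a difference, and it also depends on whether the QEEG value is a week-0 level or a change. This stands, and it makes the missing definitions part of the point.
- **The figures rest on equal SDs.** Entry requires a HAM-D-17 of at least 14, which truncates severity at entry and makes a larger endpoint SD plausible. Step 2 shows how quickly the effect then shrinks. This stands as a limit on size, not as a reason to leave the simple r alone, since the documents give no SDs either way.
- **The stakes are modest.** This is a secondary aim in a declared pilot with no alpha or power claimed for it. That is true, but the pilot's stated product is effect sizes, and those are what the carry-over distorts.

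**Conclusion.** The point holds in a conditional form. The plan gives only an unadjusted correlation for Secondary Aim 1, and under plausible but assumed conditions this lets a severity marker pass as a marker of change. With equal SDs, ρ of 0.3 to 0.5 and a QEEG-baseline correlation of 0.4, the false-positive rate is about 11% to 14% at 15 per arm, against 5% adjusted. Under the same SDs and ρ, with QEEG unrelated to baseline, the power cost for a partial r of 0.5 is about 8 to 13 points.

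A reader might go further and infer that any QEEG link with severity becomes a false link with change, or that the simple r always loses power. The documents support neither: the carry-over is attenuated and can be zero or reversed, and the power loss vanishes at high ρ or a larger endpoint SD. The higher rates of 19% to 25% apply to a pooled sample of 30, not to an analysis within each arm. Nor do the documents show that adjustment is always the safer choice.

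**What to change.** Amend the secondary-aims paragraph of Protocol VI, and carry it into the SAP, as follows:

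1. Define change on the BDI, SQ and SF-36 (difference or percentage, and between which visits), and state which QEEG value and time point is used.
2. Within each arm, regress the endpoint score on QEEG and the baseline score, or give the equivalent partial r, with a 95% CI. Report this beside the simple r with change and its CI.
3. Report the baseline and endpoint SDs, their correlation, and the QEEG-baseline correlation, so that readers can judge how much carry-over is possible.
4. Call a QEEG metric a marker of improvement only if both estimates agree, and say in advance what agreement means (for instance, same sign with both intervals excluding zero).

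The cost is a few sentences and one degree of freedom per model, with no new data. If the analysis has already been run, the adjusted estimate can be added and labelled post hoc.
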